6.3. MISSING DATA

All available data of the subjects who withdraw from the study for any reasons will be analyzed. There will be no imputation of missing data for the analysis, except for partial dates specified below.

If the date and/or time that an AE started is incomplete, the event will be considered a TEAE unless the partial dates/times give sufficient detail in order to prove that the AE started prior to the first dose in the study. In such cases the event will not be considered a TEAE.

For rollover subjects, if the date and/or time that an AE started is incomplete, the event will not be considered a Part C TEAE unless the partial dates/times give sufficient detail to prove that the AE started on or after the first dose of Part C in the study.

If the date that a medication started is incomplete, the medication will be considered as concomitant unless the partial date(s) give sufficient detail in order to prove that the medication was started and stopped prior to the day of first dose in the study. In such a case, the medication will be considered as prior medication.

For rollover subjects, if the date that a medication started is incomplete, the medication will be considered as Part C concomitant unless the partial date(s) give sufficient detail in order to prove that the medication was started and stopped prior to the day of first dose of Part C in the study.

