6.3.1. Imputation of Missing Adverse Events/Prior or Concomitant Medications

Incomplete Start Date:

Missing day and month

- If the year is the same as the year of the first dosing date, then the day and month of the first dosing date will be assigned to the missing fields.
- If the year is prior to the year of first dosing date, then December 31 will be assigned to the missing fields.
- If the year is after the year of first dosing, then January 1 will be assigned to the missing fields.

Missing day only

• If the month and year are the same as the year and month of first dosing date, then the first dosing date will be assigned to the missing day.

Syneos Health # 1006212

- If either the year of the partial date is before the year of the first dosing date or the year of the partial date and the first dosing date are the same but the month of partial date is before the month of the first dosing date, then the last day of the month will be assigned to the missing day.
- If either the year of the partial date is after the year of the first dosing date or the year of the partial date and the first dose date are the same but the month of partial date is after the month of the first dosing date, then the first day of the month will be assigned to the missing day.
- If the stop date is not missing, and the imputed start date is after the stop date, the start date will be imputed by the stop date.

Missing day, month, and year

• No imputation is needed, and the corresponding AE will be included as a TEAE of all study parts to which it is applicable.

Incomplete Stop Date:

If the imputed stop date is before the start date, then the imputed stop date will be equal to the start date.

Missing day and month

- If the year of the incomplete stop date is the same as the year of the last dosing date, then the day and month of the last dosing date will be assigned to the missing fields.
- If the year of the incomplete stop date is prior to the year of the last dosing date or prior to the year of the first dosing date, then December 31 will be assigned to the missing fields.
- If the year of the incomplete stop date is prior to the year of the last dosing date but is the same as the year of the first dosing date, then the first dosing date will be assigned to the missing date.
- If the year of the incomplete stop date is after the year of the last dosing date, then January 1 will be assigned to the missing fields.

Missing day only

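### For rollover subjects, SAP 6.3 and 6.3.1 disagree on whether an AE with a missing or ambiguous start date is a Part C TEAE, and the 6.3 rule can only undercount

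*SAP*

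**What the plan says.** SAP 6.3 holds three rules that bear on this point.

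- **AEs in general.** With an incomplete start, "the event will be considered a TEAE unless the partial dates/times give sufficient detail in order to prove that the AE started prior" (that is, before any study dosing). The default is inclusion.
- **AEs in rollovers.** With an incomplete start, "the event will not be considered a Part C TEAE unless the partial dates/times give sufficient detail". What must be shown is onset no earlier than initial Part C dosing. The default is exclusion from Part C.
- **Medications in rollovers.** With an incomplete start, "the medication will be considered as Part C concomitant unless the partial date(s) give sufficient detail" to show that it was both started and stopped before Part C dosing. The default is inclusion.

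SAP 6.3.1 then gives the imputation rules for start dates.

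- **Day missing:** "If the month and year are the same as the year and month of first dosing date, then the first dosing date will be assigned" in place of the absent day.
- **Day and month missing:** "If the year is the same as the year of the first dosing date, then the day and month of the first dosing date" fill the gaps.
- **Everything missing:** "No imputation is needed, and the corresponding AE will be included as a TEAE of all study parts to which it is applicable".

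Section 6.3.1 does not say which first dosing date applies to a subject who has been dosed in two parts. SAP 6.2.1 defines C1D1 separately for each part in rollovers, and SAP 6.2.7 gives them a separate Part C baseline. TEAE incidence and severity in Parts A, B and C is a primary endpoint (Protocol 6.4, SAP 4.1). Protocol 14.1 and SAP 3.6 put the rollover cohort at 0 to 54 subjects.

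**The concern.** Two programmers who each follow the SAP could produce different C4 tables. An AE with no start date proves nothing about onset, so 6.3 leaves it out of Part C, while 6.3.1 puts it in. The same can happen to an AE dated only to the month or year in which Part C dosing began.

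The direction also matters. Other defaults in the SAP are inclusive: the general AE rule in 6.3, and the rule in 9.3 that a missing causality is counted as treatment-related. The rollover AE rule goes the other way, and SAP Section 11 neither lists nor explains it. Its effect falls on the tables that describe the toxicity of the combination.

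**Working it through.** No sample size, power or error rate is involved, so there is no planned figure to reproduce. The check sets the rules side by side and then counts onset days for a hypothetical rollover subject.

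**Side by side: is the event a Part C TEAE?**

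| Start date known | 6.3 rollover rule | 6.3.1, anchor = first Part C dose | 6.3.1, anchor = first study dose |
|---|---|---|---|
| Nothing | No | Yes, if Part C is applicable | Yes, if Part C is applicable |
| Only the year, same year as first Part C dose | No | Yes | No in the example below |
| Month and year, same month as first Part C dose | No | Yes | No in the example below |
| Month or year wholly after first Part C dose | Yes | Yes | Yes for a later month in the example below |

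**Inputs for the count (assumed, because the documents give no subject-level dates).** Monotherapy starts 10 Sep 2019, Part C starts 15 Mar 2020, follow-up ends 15 Dec 2020. That gives 463 possible onset days, of which 276 fall on or after the first Part C dose. Stop dates are ignored. Each onset day is classified as if part of its date were lost.

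| Missing part | True Part C days | 6.3 | 6.3.1, Part C anchor | 6.3.1, study anchor |
|---|---|---|---|---|
| Day | 276 | 259 | 290 | 259 |
| Day and month | 276 | 0 | 350 | 0 |
| Day, month and year | 276 | 0 | 463 | 463 |

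**Undercount under 6.3.** With the day missing, the rule misses the days from the first Part C dose to the end of that month: days in month − day of dose + 1.

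- 15 March: 31 − 15 + 1 = 17 of 276 (check: 276 − 259 = 17).
- 3 June 2019 (monotherapy from 4 Feb 2019, end 20 Dec 2019): 30 − 3 + 1 = 28 of 201.
- 28 March 2020 (other dates as in the main example): 31 − 28 + 1 = 4 of 263.

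With only the year known, 6.3 misses all true Part C days in these examples, because follow-up ends in the calendar year in which Part C began. An event dated to a later year would be kept. With nothing known, it misses all of them. It adds no false Part C event in any row.

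**Overcount under 6.3.1 with the Part C anchor.** Day missing: 290 − 276 = 14. Day and month missing: 350 − 276 = 74. Everything missing: 463 − 276 = 187.

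These are counts of calendar days, not expected numbers of AEs.

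**Effect on incidence.** One rollover whose only record of a given event is excluded lowers that event's C4 incidence by 100/N percentage points: 100/54 = 1.85 at the upper end of the SAP's estimate, and 100/40 = 2.5 or 100/20 = 5.0 at two smaller assumed sizes.

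**The case against.** The strongest reply has four parts.

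1. **Applicability.** Section 6.3.1 includes undated events only in the parts to which they apply, and 6.3 could be read as deciding when Part C applies. This leaves some room, but not much. Only rollovers are treated in more than one part, so a clause about all applicable parts has little work to do unless it addresses them. Under the reconciling reading it would never place an undated rollover AE in Part C.

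2. **Anchor.** With the first study dose as anchor, 6.3 and 6.3.1 agree on partial dates in the example (259 against 259, and 0 against 0). This stands. For partial dates the defect is an unnamed anchor. SAP 6.2.1 supports the Part C dose, but 6.3.1 does not state it.

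3. **Attribution.** Rollovers have already received ALKS 4230, so an inclusive default can count monotherapy events as combination toxicity; the overcounts of 14, 74 and 187 days show this. It also stands, as a cost of the fix. A fixed exclusion has the opposite error, and an inclusive default is the direction the SAP takes in its general AE rule and for missing causality.

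4. **Medications.** The medication rule asks about overlap in time, whereas TEAE status turns on onset or worsening. The different default for medications is therefore weak evidence that the AE rule is a mistake, and the point does not rest on it.

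A reader might go further and infer that 6.3 drops every incompletely dated AE in rollovers, or that such events vanish from the report. Neither is supported. Section 6.3 keeps partial dates that prove onset on or after the first Part C dose. An excluded event is still a study TEAE under the general rule unless its date proves onset before the first study dose, and SAP 9.3 lists all TEAEs with their original dates.

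**Conclusion.** The SAP should be corrected. Sections 6.3 and 6.3.1 conflict for rollover AEs with fully missing start dates under either anchor, on the natural reading of the applicability clause. They conflict for ambiguous partial dates only if the 6.3.1 anchor is the first Part C dose. Provided the recorded parts of dates are correct, the 6.3 rule can only undercount Part C TEAEs, and only in C4 and the Part C overall column.

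The size is unknown, because the documents do not say how many rollover AEs have such dates. It would therefore be too strong to say that the primary safety endpoint is undercounted; the rule allows an undercount and does not show one. A reader might also take the number of subjects at risk as the combined Part A and Part B maxima, 54 + 82 = 136. The documents do not support that. C4 requires progression after at least 2 cycles or stable disease after at least 4, together with expected tolerance of the combination, and it bars a continuing PR or CR. The stated estimate is 0 to 54. No inferential testing is planned (Protocol 14.2), so the consequence is a description of combination toxicity that may be too favourable in one cohort, not a wrong test result.

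**What to change.** Replace the rollover AE sentence in SAP 6.3 with:

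> *An AE with an incomplete start date/time is a Part C TEAE unless the available start or stop date proves that it began, without later worsening, before the first Part C dose.*

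State in SAP 6.3.1 that the first Part C dose is the anchor for Part C analyses. The stop date is needed so that an undated AE known to have ended before Part C is not counted there. The worsening clause keeps the rule in line with the TEAE definition in SAP 9.3 and Protocol 14.4.7.

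The cost is one replaced sentence and one added statement, with no new data. The downside should be disclosed: some AEs that began on monotherapy may be counted in Part C, so C4 counts may rise slightly.

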6.3.1. Imputation of Missing Adverse Events/Prior or Concomitant Medications

Incomplete Start Date:

Missing day and month

- If the year is the same as the year of the first dosing date, then the day and month of the first dosing date will be assigned to the missing fields.
- If the year is prior to the year of first dosing date, then December 31 will be assigned to the missing fields.
- If the year is after the year of first dosing, then January 1 will be assigned to the missing fields.

Missing day only

• If the month and year are the same as the year and month of first dosing date, then the first dosing date will be assigned to the missing day.

Syneos Health # 1006212

- If either the year of the partial date is before the year of the first dosing date or the year of the partial date and the first dosing date are the same but the month of partial date is before the month of the first dosing date, then the last day of the month will be assigned to the missing day.
- If either the year of the partial date is after the year of the first dosing date or the year of the partial date and the first dose date are the same but the month of partial date is after the month of the first dosing date, then the first day of the month will be assigned to the missing day.
- If the stop date is not missing, and the imputed start date is after the stop date, the start date will be imputed by the stop date.

Missing day, month, and year

• No imputation is needed, and the corresponding AE will be included as a TEAE of all study parts to which it is applicable.

Incomplete Stop Date:

If the imputed stop date is before the start date, then the imputed stop date will be equal to the start date.

Missing day and month

- If the year of the incomplete stop date is the same as the year of the last dosing date, then the day and month of the last dosing date will be assigned to the missing fields.
- If the year of the incomplete stop date is prior to the year of the last dosing date or prior to the year of the first dosing date, then December 31 will be assigned to the missing fields.
- If the year of the incomplete stop date is prior to the year of the last dosing date but is the same as the year of the first dosing date, then the first dosing date will be assigned to the missing date.
- If the year of the incomplete stop date is after the year of the last dosing date, then January 1 will be assigned to the missing fields.

Missing day only

• If the month and year of the incomplete stop date are the same as the month and year of the last dosing date, then the day of the last dosing date will be assigned to the missing day.

Syneos Health # 1006212

• If either the year of the partial date is not equal to the year of the last dosing date or the year of the partial date and the last dosing date are the same but the month of partial date is not equal to the month of the last dosing date, then the last day of the month will be assigned to the missing day.

6.4. VISIT WINDOWS

Data collected at unscheduled visits that occurred outside the time windows specified in the protocol (e.g., postdose laboratory tests done on days not specified in the protocol) will be included in the data listings but will not be included in analyses summarized by timepoint unless otherwise stated.

For summaries by time point, if data is collected at multiple time points within a protocol specified time window (protocol section 8.2), the result taken at the closest time to the planned nominal time point will be used, unless specified otherwise. If this time is equal to either side of the nominal time-point for 2 measures, the earlier measure will be taken.

6.5. POOLING OF CENTERS

Data from all study centers will be combined for analysis.

6.6. SUBGROUPS

Some analyses by subgroups are planned, for example subgroup analysis based on the tumor type.

6.7. HANDLING PHARMACODYNAMICS DATA BELOW THE LOWER LIMIT OF QUANTIFICATION OR MISSING

For pharmacodynamic immunophenotype results, serum cytokine concentration summary, individual serum cytokine concentration versus time curves, and mean concentration versus time graphs, the following rules will apply:

- Serum cytokine concentration values below the assay's lower limit of quantification (LLOQ) for all time points will be treated as ½ of the LLOQ.
- For baseline with missing values, the fold change from baseline for relevant pharmacodynamic parameters will not be calculated. The sampling time of pre-infusion samples relative to dosing will be treated as zero.
- If the actual time of sampling is missing, the nominal time will be used.
- No further imputation will be applied to any missing values.

Version V3.0

Syneos Health # 1006212

• If one or both AC values are missing at a time point for NK and T_{reg} cells or for CD8 T and T_{reg} cells, then no ratios ($R_{NK/Treg}$ or $R_{CD8/Treg}$) will be calculated for the time point.

7. DEMOGRAPHIC, OTHER BASELINE CHARACTERISTICS AND MEDICATION

7.1. SUBJECT DISPOSITION AND WITHDRAWALS

The total number of subjects enrolled to each study part will be summarized separately for Part A, Part B, and Part C. A summary of subject disposition will be presented for the Safety Population, Antitumor Evaluable Population and subjects who discontinued from the treatment and discontinued from the study.

Reasons for treatment discontinuation and study discontinuation will be summarized for all subjects with the following categories:

- Adverse event
- Lost to follow-up
- Pregnancy
- Noncompliance resulting in a protocol deviation
- Study terminated by sponsor
- Withdrawal by subject
- Progressive disease
- Clinical progression
- Physician decision
- Rollover from monotherapy to combination therapy (Part C) (this is only applied to part A and Part B disposition tables)
- Other

Subjects' completion/discontinuation status will be listed, including subject identifier, informed consent date, date of completion/early discontinuation and, for those who discontinued early, the specific reason(s) for discontinuation.

Inclusion/exclusion criteria definitions and violations will be listed. If no inclusion/exclusion violations are reported, this will be noted in place of the listing.

Major protocol deviations will be summarized by categories for all subjects. All protocol deviations related to study inclusion or exclusion criteria, conduct of the trial, subject management, or subject assessment will be listed.

Syneos Health # 1006212

7.2. DEMOGRAPHIC AND OTHER BASELINE CHARACTERISTICS

Age (years), height (cm), weight (kg), and BMI (kg/m²) at baseline will be summarized descriptively. Sex, race, ethnicity, BMI category (underweight: < 18.5 kg/m², normal: 18.5 - <25 kg/m², overweight: 25 - <30 kg/m², and obesity: \geq 30 kg/m²), and ECOG performance status (0, 1, >1) will be summarized by frequency counts. Body mass index is calculated based on weight and height at baseline.

Demographic data and baseline characteristics (as detailed above) as well as informed consent data will be listed.

Descriptive statistics for prior line of therapy will be summarized.

7.3. CANCER DISEASE HISTORY

Cancer disease history will be summarized. The number and percentage of subjects in each of the following categories will be presented.

- Method of Initial Diagnosis
- Primary Origin of Tumor Type

The time from initial diagnosis to first dose (years) and time from most recent disease progression to first dose (weeks) will be summarized descriptively.

Cancer disease history will be listed for the Safety Population.

7.4. MEDICAL HISTORY

Reported medical history terms will be coded using Medical Dictionary for Regulatory Activities (MedDRA) version 25.0 or higher. General medical history information will be summarized by category of medical history being collected. Medical history will be listed for the Safety Population.

7.5. PRIOR SURGERIES AND THERAPIES

A frequency tabulation of the number of subjects with previous cancer-related surgery, radiation therapy, and systemic therapy will be given. In addition, tabulation will be provided by location of radiation therapy and type of previous systemic therapy.

Prior cancer-related surgery, prior radiation therapy, and prior systemic therapy will be listed.

Version V3.0

Syneos Health # 1006212

7.6. PRIOR AND CONCOMITANT MEDICATION

Prior medications will be defined as any medications taken prior to the C1D1. Concomitant medications will be defined as medications ongoing or stopped on or after the date of the first dose of ALKS 4230.

Prior and concomitant medications will be coded with World Health Organization (WHO) Drug Dictionary version March 2016 or higher.

The number and percentage of subjects using each concomitant medication will be displayed together with the number and percentage of subjects using at least 1 medication within each medication group and subgroup. Prior medications will be presented in a data listing only.

Version V3.0

Syneos Health # 1006212

8. EFFICACY

Antitumor activity will be determined by the measurement of extent of known disease at baseline and approximately every 5 to 6 weeks, following each even-numbered treatment cycle. Appropriate radiological procedures (computed tomography (CT) scanning, magnetic resonance imaging (MRI), radionuclide imaging) should be conducted to evaluate areas of disease. Superficial skin tumors will be measured with calipers and photographed for evaluation. It is requested that the initial method of measurement be maintained throughout the course of the study. The determination of response will be conducted according to the standard RECIST 1.1 criteria as well as the iRECIST for part A, B, and C.

According to the guidelines for RECIST 1.1, tumors are assessed as complete response (CR), partial response (PR), stable disease (SD), or progressive disease (PD).

Responses assigned using iRECIST have a prefix of "i" e.g., "immune" complete response (iCR) or partial response (iPR), stable disease (iSD), and unconfirmed progressive disease (iUPD) or confirmed progressive disease (iCPD) to differentiate them from responses assigned using RECIST 1.1.

RECIST 1.1 and iRECIST have the same overall response until RECIST 1.1 progressive disease (PD) is reached. The iRECIST CRF will be used if patient has a RECIST disease progression and clinical stable, and continues on treatment. The principles used to establish objective tumour response are largely unchanged from RECIST 1.1, but the major change for iRECIST is the concept of resetting the bar if RECIST 1.1 progression is followed at the next assessment by tumour shrinkage. iRECIST defines iUPD on the basis of RECIST 1.1 principles; however, iUPD requires confirmation.

As the iRECIST CRF page is only triggered after patients has iUPD and clinical stable. In the process to create iRECIST analysis dataset, the tumor response data before iUPD will be copied from RECIST 1.1

To note, determination of response is conducted according to iRECIST beginning with Amendment 10. Prior to Amendment 10 it was conducted by IrRC.

In studies with immunotherapeutic agents, CR, PR, or SD have been shown to occur after an increase in tumor burden characterized as PD by RECIST criteria. The conventional response criteria such as RECIST may not adequately assess the activity of immunotherapeutic agents. PD evaluated radiologically may not mean therapeutic failure, as responses to immune therapies may occur after conventional PD. The appearance of measureable antitumor activity may take longer for immune therapies than for cytotoxic therapies. With immunotherapeutic agents, there should be allowance for clinically insignificant PD, defined as small new lesions in the presence of other responsive lesions, which may occur even though the subject is responding to the immunotherapy. Stable disease may also represent antitumor activity with iRECIST. Therefore, RECIST and

Version V3.0

Syneos Health # 1006212

iRECIST will be used to ensure a more comprehensive evaluation of tumor response for ALKS 4230.

Efficacy endpoints based on irRC and iRECIST will not be derived and associated analyses will not be performed as the iRECIST was implemented during the middle of the study conduct to replace irRC. The sites have not consistently record the iRECIST data which could provide misleading information.

